10.2.3.4 Neutropenia

- **Incidence and Event Rate of Neutropenia TEAEs per 100 subject years by SOC, HLT and PT**

This table will be based on the following PTs (regardless of seriousness):

- Autoimmune neutropenia
- Band neutrophil count decreased
- Cyclic neutropenia
- Febrile neutropenia
- Idiopathic neutropenia
- Neutropenia
- Neutropenic infection
- Neutropenic sepsis
- Neutrophil count decreased

10.2.3.5 Suicidal Ideation and Behavior

- **Incidence and Event Rate of SIB-Adjudicated Neuropsychiatric TEAEs per 100 subject years by SOC, HLT and PT**

An external neuropsychiatric adjudication committee will evaluate potential neuropsychiatric events and determine whether any of those events were associated with suicidal ideation and behavior (SIB). If an event is adjudicated as SIB, further information will be provided. A table and listing for SIB events as determined by the adjudication committee will be included.

Additionally, a listing of all events identified for potential review by the neuropsychiatric adjudication committee will be produced. This listing will indicate whether each event was escalated to the committee for formal review/adjudication. A separate listing will also be produced to summarize the adjudicated results of all events escalated to the full committee.

10.2.3.6 Inflammatory bowel disease

- **Incidence and Event Rate of Inflammatory Bowel Disease TEAEs per 100 subject years by SOC, HLT and PT**

These events will be presented in a stand-alone table which will include all TEAEs which code into the HLT of “Colitis excl infective”.

Inflammatory bowel disease events will be summarized stratified by subjects with or without a previous medical history of inflammatory bowel disease. Previous medical history of inflammatory bowel disease will be determined using the information recorded on the Extra-Articular Assessment at Screening CRF page (“Does subject have a history of IBD?”).

10.2.3.7 Hypersensitivity (including anaphylaxis)

- **Incidence and Event Rate of Anaphylactic Reaction TEAEs per 100 subject years by SOC, HLT and PT**

A separate table will be prepared based on the MedDRA anaphylaxis Algorithm (see Appendix 1) for acute anaphylactic events (reported on the same day as when an injection was administered or one day after). An AE glossary table will also be produced to summarize the MedDRA coding for these events. The glossary table will include the following fields: reported term, PT, LLT, HLT, and SOC.

- **Incidence and Event Rate of Hypersensitivity Reaction TEAEs per 100 subject years by SOC, HLT and PT**

A separate table will be prepared to summarize hypersensitivity events, identified using the SMQ “Hypersensitivity (SMQ)”. All TEAEs which code to a PT included in the Scope=Narrow search will be included in this table. An AE glossary table will also be produced to summarize the MedDRA coding for these events. The glossary table will include the following fields: reported term, PT, LLT, HLT, and SOC.

Furthermore, injection site reactions will be evaluated based on the any TEAE table (no separate table needed) by looking under the following HLTs: “Administration site reactions NEC” and “Injection site reactions”.

10.2.3.8 Hepatic events

- **Incidence and Event Rate of Hepatic Events TEAEs per 100 subject years by SOC, HLT and PT**

A table for hepatic events will be created based on the SMQ of “Drug related hepatic disorders - comprehensive search (SMQ)”. However, these 2 sub-SMQs are to be excluded: “Liver neoplasms, benign (incl cysts and polyps) (SMQ)” and “Liver neoplasms, malignant and unspecified (SMQ)”.

Note that all AEs meeting the above criteria are to be included. It should not be limited to events that the investigator determined to be related to study drug.

Cases of Hy’s Law will be reported separately in a liver function test table (with adjudication for “potential DILI” confirmation).

A by-subject listing of all AE of safety topics of interest by type of safety topics of interest will be provided.

10.3 Clinical laboratory evaluations

Laboratory values, including markedly abnormal laboratory values will be presented descriptively by treatment group for SS up to Week 56. Markedly abnormal values and shifts from baseline (Week 0) will be presented for the SS through Week 24 and BKZ set through initial and maintenance treatment period.

The markedly abnormal tables and those based on CTCAE grade will be produced only for selected laboratory variables.

For tables where data are summarized by visit, unscheduled and repeat visits will not be summarized, but these data will be included in listings. For tables where multiple measurements over a period of time are considered (as in shift tables), unscheduled and repeat visits will be considered as long as they were collected in the period being summarized. All summaries will be presented in SI units and will be based on observed case values. In the case where laboratory values are below the lower limit of quantification, then these will be set to the midpoint between 0 and the lower limit of quantification for the purpose of summarizing the data. The following summaries are required:

- A summary of the absolute and change from Baseline values in each laboratory variable by treatment group and visit
- A summary of the number and percentage of subjects experiencing markedly abnormal values at any time while on treatment (assessment on or following the first dose of study treatment through the final dose of study treatment + 140 days) by laboratory variable and treatment group
- A summary of the number and percentage of subjects with a given CTCAE grade (0, 1, 2, 3, or 4) based on minimum/maximum post-baseline value by laboratory variable and treatment group
- A shift table of the number and percentage of subjects experiencing CTCAE grade 0, 1, 2, 3 or 4 values (as applicable) at Baseline to minimum/maximum post-Baseline CTCAE grade, by laboratory variable and treatment group

For laboratory summaries through week 24, the cut off will be the earliest of week 24 or last dose + 140 days.

For laboratory shift tables through week 24, the treatment groups BKZ 320mg Q4W, BKZ 320mg Q4W/Q8W, BKZ Total and ADA will be presented.

For laboratory shift tables through initial and maintenance treatment period, the treatment groups BKZ 320mg Q4W, BKZ 320mg Q4W/Q8W, ADA/ BKZ 320 mg Q4W and BKZ Total will be presented. For subjects randomized to ADA, only data after the switch to Bimekizumab will be considered. The last value prior to the switch will be considered as baseline.

A by-subject listing of all laboratory data will be provided. This listing will be presented by treatment group and will include: center, subject identifier, age, sex, race, weight, visit, laboratory variable, result (with abnormal values flagged as “L” or “H” accordingly) and unit.

Markedly abnormal values are defined as those with a severity of Grade 3 and above based on the common terminology criteria for adverse events (CTCAE) criteria (U.S. Department of Health and Human Services 2010). Definitions of markedly abnormal values using the Grade 3 cut points are given in the tables below for age ranges of ≥ 17 years (Table 10–1 for markedly abnormal biochemistry values and Table 10–2 for markedly abnormal hematology values).

Tables summarizing markedly abnormal values should include a summary (counts and percentages) of markedly abnormal labs observed at any time while on treatment (ie, treatment-emergent markedly abnormal [TEMA]). For this summary, Baseline values and values observed more than 140 days after the last administration of study medication are not considered. The laboratory results classified as Grade 3 or Grade 4 will be summarized and listed separately.

Summaries in the ADA/BKZ arm will be provided to examine markedly abnormal labs occurring within 70 days and >70 days of the treatment switch. The time since the treatment switch is calculated as the number of days since the final dose of adalimumab. Only lab values recorded after the start of bimekizumab treatment will be included. 70 days was chosen as it is approximately equal to five half lives of adalimumab.

Table 10–1: Definitions of Markedly Abnormal Biochemistry Values

Parameter name	Conventional		Standard		Abnormal Designation
	Unit	Criteria	Unit	Criteria	
Creatinine	mg/dL	>3.0 x ULN	mmol/L	>3.0 x ULN	AH
Glucose	mg/dL	<40 >250	mmol/L	<1.7 >13.9	AL AH
Calcium	mg/dL	>12.5 <7.0	mmol/L	>3.1 <1.75	AH AL
Magnesium	mg/dL	>3.0 <0.9	mmol/L	>1.23 <0.4	AH AL
Potassium	mmol/L	>6.0 <3.0	mmol/L	>6.0 <3.0	AH AL
Sodium	mmol/L	>155 <130	mmol/L	>155 <130	AH AL

Table 10–2: Definitions of Markedly Abnormal Hematology Values

Parameter name	Conventional		Standard		Abnormal Designation
	Unit	Criteria	Unit	Criteria	
Hemoglobin	g/dL	<8.0 >4.0 above ULN	g/L	<80 >40 above ULN	AL AH
Lymphocytes Absolute	10 ⁹ /L	<0.5 >20.0	10 ⁹ /L	<0.5 >20.0	AL AH
Neutrophils Absolute	10 ⁹ /L	<1.0	10 ⁹ /L	<1.0	AL
Platelets	10 ⁹ /L	<50	10 ⁹ /L	<50	AL
WBC/Leukocytes	10 ⁹ /L	<2.0 >100	10 ⁹ /L	<2.0 >100	AL AH

Abbreviations: AH=abnormal high; AL=abnormal low; ALT= alanine aminotransferase; AST = aspartate aminotransferase; dL = deciliter; GGT: gamma-glutamyltransferase; L = liter; mg = milligram; mmol = millimoles; µg = microgram; ULN = upper limit of normal.

The following criteria will be considered for summaries of markedly abnormal liver function tests (LFTs):

- AST: >3xULN, >5xULN, >8xULN, >10xULN, >20xULN
- ALT: >3xULN, >5xULN, >8xULN, >10xULN, >20xULN

- AST or ALT: >3xULN, >5xULN, >8xULN, >10xULN, >20xULN
- Bilirubin: >1.5xULN, >2xULN

In addition, a table will be produced to summarize potential Hy’s Law cases. The following definition will be used in that table:

- [AST \geq 3xULN or ALT \geq 3xULN] and Total Bilirubin \geq 2xULN in the absence of ALP \geq 2xULN

In order to meet the above criteria, a subject must experience the elevation in bilirubin and ALT or AST (and the absence of ALP elevation) at the same visit. For example, a subject who experiences a \geq 2 x ULN elevation of bilirubin at one visit and a \geq 3xULN elevation in ALT (or AST) at a subsequent visit has not fulfilled the Hy’s law criteria.

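### SAP Table 10-1 prints two different concentrations, <40 mg/dL and <1.7 mmol/L, for one low-glucose cut-off

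*SAP*

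**What the plan says.** SAP Section 10.3 ties the term to a grading scale: "Markedly abnormal values are defined as those with a severity of Grade 3 and above" under CTCAE, which the SAP's reference list gives as Version 4.0 of June 2010. It continues: "Definitions of markedly abnormal values using the Grade 3 cut points are given in the tables below".

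Table 10-1, titled "Definitions of Markedly Abnormal Biochemistry Values", has a conventional and a standard unit column, with one designation (abnormal low or abnormal high) per limit. Its Glucose row reads <40 and >250 mg/dL in the conventional column, and <1.7 and >13.9 mmol/L in the standard column.

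On units, Section 10.3 says: "All summaries will be presented in SI units and will be based on observed case values". On scope: "The markedly abnormal tables and those based on CTCAE grade will be produced only for selected laboratory variables". Glucose is one of the six parameters in Table 10-1.

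The markedly abnormal flag feeds these outputs:

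- the count of subjects per arm with such a value on treatment, for the Safety Set through Week 24 and for the Bimekizumab Set through the initial and maintenance periods;
- the summaries for subjects who switch from adalimumab, split at 70 days after their final adalimumab dose.

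The appendix table of CTCAE biochemistry grades (Table 12-1) is in mmol/L and has no glucose row. Neither SAP amendment log records a change to the glucose limits.

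**The concern.** The two columns should express one threshold in two unit systems. If they disagree, the SAP does not define a single count of subjects with markedly low glucose. Two programmers, one working from each column, could follow the plan faithfully and report different numbers. Since summaries are in SI units, the figure more likely to be used is the stricter one, <1.7 mmol/L, and low-glucose cases could then be under-counted in a safety table.

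**Working it through.** **Inputs.** All cut-offs are from SAP Table 10-1. The molar masses (glucose 180.156, calcium 40.078, magnesium 24.305 g/mol) are physical constants and not figures from the documents.

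**Step 1: the table's own conversion factor.** The high-glucose pair gives 250 / 13.9 = 17.99 mg/dL per mmol/L. Applied to the low pair:

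- 40 / 17.99 = 2.22 mmol/L, against a printed 1.7;
- 1.7 × 17.99 = 30.6 mg/dL, against a printed 40.

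The low pair by itself implies 40 / 1.7 = 23.53 mg/dL per mmol/L, which contradicts the 17.99 in the same row.

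**Step 2: every pair that needs conversion.** The formula is mmol/L = mg/dL × 10 / molar mass.

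| Limit | mg/dL | Printed mmol/L | Converted mmol/L | Printed vs converted |
|---|---|---|---|---|
| Glucose low | 40 | 1.7 | 2.220 | −23.4% |
| Glucose high | 250 | 13.9 | 13.877 | +0.2% |
| Calcium high | 12.5 | 3.1 | 3.119 | −0.6% |
| Calcium low | 7.0 | 1.75 | 1.747 | +0.2% |
| Magnesium high | 3.0 | 1.23 | 1.234 | −0.3% |
| Magnesium low | 0.9 | 0.4 | 0.370 | +8.0% |

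The magnesium difference is rounding: 0.370 is 0.4 to one decimal. Low glucose is not: 2.220 is 2.2 to one decimal and 2.22 to two, so no rounding gives 1.7.

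**Step 3: can the SAP itself settle it?** For creatinine, sodium, potassium, calcium and magnesium, the standard-column limits in Table 10-1 equal the Grade 3 bounds in Table 12-1. Glucose is the only Table 10-1 parameter without a row there, so this check cannot be made for it.

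**Step 4: what follows.** The gap runs from 1.7 up to 2.22 mmol/L (30.6 up to 40 mg/dL), a width of 2.22 − 1.70 = 0.52 mmol/L. If one of the two printed limits is the intended one:

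| Intended limit | Column that drives the flag | Subjects whose lowest on-treatment value is in the gap |
|---|---|---|
| <40 mg/dL | Standard | Wrongly left out |
| <40 mg/dL | Conventional | Correctly counted |
| <1.7 mmol/L | Standard | Correctly left out |
| <1.7 mmol/L | Conventional | Wrongly counted |

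The output counts subjects who ever meet the criterion. A subject who also has a reading below 1.7 mmol/L is counted under either limit. Only subjects whose lowest value falls in the gap are affected.

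**The case against.** The strongest case on the other side concerns size and certainty, not the arithmetic.

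- **Which cell is wrong is not shown.** A reader might infer that 1.7 mmol/L is the error and that the plan will miss low-glucose cases. The documents do not support that. The controlling definition is CTCAE Grade 3, and neither document prints the CTCAE glucose grades. This objection stands.
- **The SI sentence is about presentation.** It does not say which column derives the flag. Use of the standard column is an inference. It is a natural one, since Table 12-1 is also in mmol/L, but it is not a stated rule. This stands too.
- **The values do not disappear.** Section 10.3 also plans by-visit summaries of absolute values and changes from Baseline, and a by-subject listing of all laboratory data with low and high results flagged. A reading of 2.0 mmol/L would still be listed. Only the markedly abnormal count is at issue.
- **The gap in Table 12-1 is not in itself an error.** A reader might take the missing glucose row as a second fault. Section 10.3 restricts the graded tables to selected variables, and the omission is consistent with that.
- **Little hangs on it.** Glucose is not among the safety topics of interest in Protocol Section 12.1.1.4 or SAP Section 10.2.3. No endpoint, hypothesis test, eligibility criterion or withdrawal criterion uses this cut-off.

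These points limit the consequence. None of them makes the two cells equal.

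**Conclusion.** The point holds in limited form. The two low-glucose cells are different concentrations, with the standard figure about 23% below the converted conventional one, so at least one is wrong as printed. No current text explains the difference, and the agreement of the neighbouring pairs makes a general conversion problem or a scrambled table unlikely.

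An under-count rests on three assumptions: that <40 mg/dL is the intended Grade 3 limit, that the standard column drives the flag, and that glucose is among the selected variables, as its place in Table 10-1 suggests. If <1.7 mmol/L is the intended limit, the conventional cell is the error, and counts taken from the standard column would be right. The number of subjects affected cannot be derived from the documents and may be zero.

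This is a minor correction to a descriptive safety table.

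**What to change.** 1. Look up the Grade 3 limit for low glucose in the CTCAE version that the SAP cites.
2. Correct Table 10-1 so that both columns give that concentration. If <40 mg/dL is confirmed, the standard cell becomes <2.2 mmol/L. Rounding 2.22 to 2.2 leaves a sliver of 0.02 mmol/L, which is of the same order as the rounding elsewhere in the table.
3. State in Section 10.3 which column derives the flag, and check that the program uses the corrected value.

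Adding glucose to Table 12-1 is optional. It would help if glucose is meant to be part of the separate Grade 3 and Grade 4 reporting that Section 10.3 plans, since the SAP gives no Grade 4 limit for it.

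The cost is one table cell, one sentence and a one-line program check. No data collection or sample size changes.

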5.2.3 Dose-blind Maintenance Treatment Period

After the 16-week Initial Treatment Period, subjects will enter the 40-week Maintenance Treatment Period. Treatment during the Maintenance Treatment Period will start at Week 16 and subjects will return to the clinic Q4W or Q8W through Week 56. The IMP will be administered in the clinic by sc injection at the time points specified in the schedule of study assessments (Table 5-1). Treatment during the Maintenance Treatment Period will be based on initial treatment per the following:

- Subjects in the bimekizumab 320mg Q4W treatment arm will continue to receive bimekizumab 320mg Q4W.
- Subjects in the bimekizumab 320mg Q4W/Q8W treatment arm will receive bimekizumab Q8W from Week 16 through Week 52.
- Subjects in the adalimumab treatment arm will receive bimekizumab 320mg Q4W from Week 24 to Week 52.

Subjects may receive placebo injections at certain visits in order to blind the IMP (see Section 7.2).

At the end of the Maintenance Treatment Period, all subjects enrolling in the open-label study will, after signing a new ICF, undergo the Week 56 study assessments and then receive their first dose of bimekizumab in the open-label study. All subjects not enrolling in the open-label study will have the Week 56 study assessments and will enter the SFU Period.

The assessments to be performed at each visit of the Maintenance Treatment Period are presented in Table 5-1.

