5.8 Rationale for study design and selection of dose

5.8.1 Study design

A randomized, active-controlled study design has been selected to demonstrate efficacy and safety of bimekizumab for regulatory approval. The study population will include adults with moderate to severe chronic plaque PSO and allow subjects who have received previous biologic treatment as well as those who are biologic treatment naïve. The primary efficacy outcome measures (based on PASI and IGA) and other efficacy assessments included in this study are consistent with those used for other PSO studies and are considered appropriate for establishing efficacy of bimekizumab. An Initial Treatment Period of 16 weeks will be used to demonstrate the efficacy of bimekizumab compared with adalimumab. The study duration extends beyond the Initial Treatment Period (to 56 weeks) to allow for collection of long-term safety and efficacy data.

At Week 24, subjects on adalimumab treatment are re-allocated to treatment with bimekizumab 320mg Q4W. This allows for a controlled evaluation of the safety and efficacy of switching from a product with one mechanism of action to another, which is known to occur in clinical practice due to either loss of response or access. In a recent PSO study in which subjects were switched from adalimumab to a treatment with a different mechanism of action, there was no evidence of an increased safety risk following the switch without washout (Reich et al, 2017).

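### The full-period laboratory shift table in SAP 10.3 sets worst grades from 5 scheduled draws after the switch beside worst grades from 13 draws in the continuous bimekizumab arms

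*SAP*

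**What the plan says.** SAP 10.3 presents laboratory shifts for the "BKZ set through initial and maintenance treatment period". In that table, "the treatment groups BKZ 320mg Q4W, BKZ 320mg Q4W/Q8W, ADA/ BKZ 320 mg Q4W and BKZ Total will be presented". The statistic is the number and percentage of subjects moving from their grade "at Baseline to minimum/maximum post-Baseline CTCAE grade, by laboratory variable and treatment group".

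For subjects who began on adalimumab the window is cut: "For subjects randomized to ADA, only data after the switch to Bimekizumab will be considered". Their reference point moves too: "The last value prior to the switch will be considered as baseline". The switch is at Week 24; Protocol 5.2.3 says "Subjects in the adalimumab treatment arm will receive bimekizumab 320mg Q4W from Week 24 to Week 52". Unscheduled draws also enter, since "unscheduled and repeat visits will be considered as long as they were collected in the period being summarized".

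SAP 10.3 gives no exposure adjustment and no common window for this table. Exposure-adjusted rates are defined in SAP 10.2.1 for adverse events only. The separate shift table through Week 24 does use one window for all its columns.

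SAP 10.3 does not say which arms BKZ Total contains. The BKZ Set definition (SAP 3.5.5) and SAP 3.6 imply that switchers are in it. SAP Section 8 (efficacy) uses the same label for the two continuous arms only.

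**The concern.** A worst-ever percentage rises with the number of times a subject is tested and with the time over which testing runs. Here the columns differ in both, for reasons of design and not of drug effect. Someone reading across the row could take a lower percentage in switchers as evidence about switching, when some or all of the gap could come from fewer chances to detect an abnormality.

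Protocol 5.8.1 justifies the switch with the words "This allows for a controlled evaluation of the safety and efficacy of switching", and Protocol 14.5.1 singles out its safety. This is the only shift table in SAP 10.3 that places switchers beside subjects on bimekizumab throughout. BKZ Total carries the same problem if it mixes subjects with 13 and with 5 scheduled draws.

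**Working it through.** The plan states no figure for this table, so there is none to reproduce.

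**1. Count the scheduled hematology and biochemistry draws** (visit lists, Protocol 8.2.2 to 8.3.12; none is listed at Weeks 36, 44 or 52).

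| Column | Post-baseline draws (study week) | Number | Window |
|---|---|---|---|
| BKZ Q4W and BKZ Q4W/Q8W | 1, 3, 4, 8, 12, 16, 20, 24, 28, 32, 40, 48, 56 | 13 | 56 weeks |
| ADA/BKZ Q4W | 28, 32, 40, 48, 56 | 5 | 56 − 24 = 32 weeks |

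The Week 24 draw is the switchers' baseline, so it is not counted for them. The counts are for full follow-up without unscheduled draws.

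**2. Direction.** Subtract 24 from the switcher weeks to get time since first bimekizumab dose: 4, 8, 16, 24 and 32. All five are also draw weeks in the continuous arms. If the risk at each time since first dose is the same, a maximum or minimum over a subset of draws cannot be more extreme than one over the full set. The expected switcher percentage therefore cannot exceed the continuous one, whatever the time pattern or correlation.

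**3. Size, independent draws.** The risk per draw, p, is an assumption; the documents give none. P(at least one abnormal draw) = 1 − (1 − p)^n. At p = 1%: 1 − 0.99^5 = 4.9% and 1 − 0.99^13 = 12.2%. With 1:1:1 allocation and switchers included, BKZ Total = (2 × continuous + switcher)/3 = (2 × 12.2 + 4.9)/3 = 9.8%.

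| p per draw | Switchers (5) | Continuous (13) | Ratio | BKZ Total |
|---|---|---|---|---|
| 0.5% | 2.5% | 6.3% | 2.55 | 5.0% |
| 1% | 4.9% | 12.2% | 2.50 | 9.8% |
| 2% | 9.6% | 23.1% | 2.40 | 18.6% |
| 5% | 22.6% | 48.7% | 2.15 | 40.0% |

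Total lies 18% to 20% below the continuous arms in these rows.

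**4. Size, correlated draws.** Draws on one subject are unlikely to be independent. With a beta-binomial model of mean 1% and intraclass correlation ρ, P(at least one) = 1 − B(a, b + n)/B(a, b), where a = 0.01(1 − ρ)/ρ, b = 0.99(1 − ρ)/ρ and B is the beta function.

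| ρ | Switchers | Continuous | Ratio |
|---|---|---|---|
| 0.1 | 4.1% | 8.0% | 2.0 |
| 0.3 | 3.0% | 4.8% | 1.6 |
| 0.5 | 2.3% | 3.1% | 1.4 |
| 0.8 | 1.4% | 1.7% | 1.2 |

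**5. Other checks.**
- Constant hazard in time, assuming 10% over 56 weeks: 1 − 0.90^(32/56) = 5.8% over 32 weeks, a ratio of 1.7.
- One Safety Follow-Up draw added to each arm (6 against 14, p = 1%): 5.9% against 13.1%.
- Abnormalities that appear by the fourth week on bimekizumab and persist are caught by both schedules, so the gap is near nil.

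**6. What removes the gap.** Cutting the continuous arms at 32 weeks is not enough: they still have 10 draws (Weeks 1, 3, 4, 8, 12, 16, 20, 24, 28 and 32), giving 9.6% against 4.9% at p = 1%. Keeping only their draws at Weeks 4, 8, 16, 24 and 32 leaves 5 draws in every arm, and 4.9% in every column and in Total.

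**The case against.** The SAP hides nothing here. It states the post-switch window and the reset baseline, gives switchers their own column, and presents the table descriptively. Nor is this table the main vehicle for the switching question. Protocol 14.5.1 promises extra summaries, and the SAP supplies them: adverse event tables for switchers by onset up to or beyond 70 days from the last adalimumab dose (SAP 10.2.1 and 10.2.2), and the same split for markedly abnormal laboratory values in the ADA/BKZ arm (SAP 10.3). All of this stands and limits the weight of the point. None of those summaries, however, sets switchers' laboratory results beside the continuous arms on equal terms.

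The size is also open to challenge. Independent draws give the widest gaps shown above, and 1% per draw is not tied to any grade. If Grade 3 or 4 risk were 0.1% per draw (assumed), the gap would be 1.3% against 0.5%, about one subject in 150. This stands as well.

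A reader might infer that switchers are bound to look about two and a half times safer. The documents do not support that: the direction holds in expectation under equal risk and full follow-up, and the factor rests on assumed inputs. Unscheduled draws count, early dropouts in the continuous arms have fewer draws, and switchers have stayed to Week 24 with a baseline taken on adalimumab.

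A reader might also conclude that the switcher column should be deleted, or that all arms should be compared over Weeks 28 to 56. Deletion would drop up to about 150 exposed subjects whom SAP 3.5.5 and 3.6 place in the bimekizumab safety data. A common calendar window would set new starters against arms with 24 weeks of bimekizumab behind them and an on-treatment baseline, exchanging one imbalance for another. Nor does the point extend to every CTCAE table, because SAP 10.3 names the ADA/BKZ column for shift tables only.

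**Conclusion.** The point holds as one of presentation. In the full-period shift table, crude worst-grade percentages from 5 scheduled draws over 32 weeks stand beside those from 13 draws over 56 weeks. With equal risk at each time since first bimekizumab dose, the switcher column is expected to be no higher than the continuous columns, and a BKZ Total that includes switchers is pulled down.

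The draw counts and windows come from the documents; the size does not. For an assumed 1% risk per draw, the ratio of continuous to switcher percentages runs from about 2.5 with independent draws to 1.2 at within-subject correlation 0.8. No hypothesis test depends on this table. A reader might take BKZ Total as the rate over a full course of bimekizumab, but no section presents it as that; what is missing is a statement of its composition.

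**What to change.** Keep the planned table and amend SAP 10.3 as follows.

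- State which arms BKZ Total contains, and also show a Total for the two arms followed from Week 0.
- Footnote the unequal follow-up (13 against 5 scheduled draws; 56 against 32 weeks).
- Add one shift table matched on time since first bimekizumab dose. Baseline is the last value before that dose. Post-baseline values are the scheduled draws 4, 8, 16, 24 and 32 weeks after it: study Weeks 4, 8, 16, 24 and 32 in the continuous arms, and Weeks 28, 32, 40, 48 and 56 in switchers.
- Name BKZ Q4W as the like-for-like comparator, because the Q4W/Q8W arm changes interval at Week 16.

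The cost is SAP wording, one repeat of an existing table shell and a few pages of output, with no new data. The matched table leaves out unscheduled draws and the extra early draws, which remain in the planned table. It does not make the groups fully comparable: its footnote should say that switchers had stayed to Week 24 and have a baseline taken on adalimumab.
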